### **8.3 Labeling**

Labels will be prepared in accordance with Good Manufacturing Practice (GMP) and local regulatory guidelines. The labels will fulfil GMP Annex 13 requirements for labeling. Label text will be translated into local language.

Labels will be provided as a single panel label.

### **8.4 Storage**

The Investigator, or an approved representative (eg, pharmacist), will ensure that all IP is stored in a secured area, in refrigerated temperatures (2° C to 8° C) and in accordance with applicable regulatory requirements. A temperature log will be used to record the temperature of the storage area. Temperature excursions outside the permissible range listed in the clinical supply packaging are to be reported to the monitor upon detection. A calibrated temperature monitoring device will be used to record the temperature conditions in the drug storage facility. Storage conditions stated in the IB may be superseded by the label storage.

The package inserts for etoposide/carboplatin/cisplatin specifies the appropriate storage for these agents.

### **8.5 Compliance**

The administration of each study drug should be recorded in the appropriate sections of the eCRF.

Treatment compliance will be assured by reconciliation of site drug accountability logs.

### **8.6 Accountability**

The study drug provided for this study will be used only as directed in the study protocol. The study personnel will account for all study drugs.

Drug accountability should be performed until the patient stops study treatment completely. Study site personnel will account for all study drugs received at the site, for all unused study drugs, and for appropriate destruction of study drugs. Certificates of delivery, destruction, and return should be signed.

### **8.7 Concomitant medications and other treatments**

The investigator must be informed as soon as possible about any medication taken from the time of Screening until the end of the clinical treatment phase of the study (final study visit), including the Follow-up period [REDACTED]. Any concomitant medication(s), including herbal preparations, taken during the study will be recorded in the eCRF.

Patients must be instructed not to take any medications, including over-the-counter products, without first consulting with the investigator.

Restricted, prohibited, and permitted concomitant medications are described in Table 7 and

Table 8. Refer also to the Dosing Modification and Toxicity Management Guidelines (see section 7.9.1 and Annex to Protocol).

**Table 7 Prohibited concomitant medications**

| Prohibited medication/class of drug:  | Usage:  |
|--|--|
| Investigational anticancer therapy other than those under investigation in this study  | Should not be given concomitantly while the patient is on study treatment  |
| mAbs against CTLA-4, PD-1, or PD-L1 other than those under investigation in this study   | Should not be given concomitantly while the patient is on study treatment  |
| Any concurrent chemotherapy, radiotherapy, immunotherapy, or biologic or hormonal therapy for cancer treatment other than those under investigation in this study  | Should not be given concomitantly while the patient is on study treatment. (Concurrent use of hormones for non-cancer-related conditions [eg, insulin for diabetes and hormone replacement therapy] is acceptable. Local treatment of isolated lesions, excluding target lesions, for palliative intent is acceptable [eg, by local surgery or radiotherapy])  |
| Live attenuated vaccines   | Should not be given through 30 days after the last dose of IP  |
| Immunosuppressive medications including, but not limited to, systemic corticosteroids at doses exceeding 10 mg/day of prednisone or equivalent, methotrexate, azathioprine, and tumor necrosis factor- $\alpha$ blockers | Should not be given concomitantly, or used for premedication prior to the immuno-oncology infusions. The following are allowed exceptions: 
 
• Use of immunosuppressive medications for the management of IP-related AEs.
 
• Short-term premedication for patients receiving combination agents SoC, in which the prescribing information for the agent requires the use of steroids for documented hypersensitivity reactions.
 
• Use in patients with contrast allergies.
 
• In addition, use of inhaled, topical, and intra-nasal corticosteroids is permitted.
 
 
A temporary period of steroids will be allowed if clinically indicated and considered to be essential for the management of non-immunotherapy related events experienced by the patient (eg, chronic obstructive pulmonary disease, radiation, nausea, etc).
 |

| Prohibited medication/class of drug:                          | Usage:   |
|--|---|
| EGFR TKIs  | [REDACTED]
[REDACTED]
Increased incidences of pneumonitis (with third generation EGFR TKIs) and increased incidence of transaminase increases (with 1 st generation EGFR TKIs) has been reported when durvalumab has been given concomitantly. |
| Herbal and natural remedies which may have immune-modulating effects | Should not be given concomitantly unless agreed by the Sponsor  |

AE Adverse event; CTLA-4 Cytotoxic T-lymphocyte-associated antigen 4; EGFR Epidermal growth factor receptor; IP Investigational product; PD-1 Programmed cell death 1; PD-L1 Programmed cell death ligand 1; SoC Standard of care; TKI Tyrosine kinase inhibitor.

**Table 8 Supportive medications**

| Supportive medication/class of drug:  | Usage:  |
|--|--|
| Concomitant medications or treatments (eg, acetaminophen or diphenhydramine) deemed necessary to provide adequate prophylactic or supportive care, except for those medications identified as “prohibited,” as listed above                              | To be administered as prescribed by the Investigator |
| Best supportive care (including antibiotics, G-CSF and other hematopoietic factors, nutritional support, correction of metabolic disorders, optimal symptom control, and pain management [including palliative radiotherapy to non-target lesions, etc]) | Should be used, when necessary, for all patients     |
| Inactivated viruses, such as those in the influenza vaccine  | Permitted  |

### 8.7.1 Other concomitant treatment

Other medication other than that described above, which is considered necessary for the patient’s safety and wellbeing, may be given at the discretion of the physician and recorded appropriately.

### 8.7.2 Durvalumab drug-drug interactions

There is no information to date on drug-drug interactions with durvalumab either preclinically or in patients. As durvalumab is a monoclonal antibody and therefore a protein, it will be degraded to small peptides and amino acids and will be eliminated by renal and reticuloendothelial clearance. It is therefore not expected that durvalumab will induce or inhibit the major drug metabolising cytochrome P450 pathways. As a result, there are no expected pharmacokinetic drug-drug interactions. The mechanism of action of durvalumab

involves binding to PD-L1, and therefore significant pharmacodynamic drug interactions with the commonly administered concomitant medications are not expected. Despite this, appropriate clinical monitoring in all of the planned clinical studies will be conducted to evaluate any potential drug-drug interactions.

## 8.8 Rescue medication

As a result of imAEs that could potentially be experienced by patients on durvalumab, steroids and other immunosuppressant rescue medication has to be made available to this patient population. The 2 products that fall into the category of immunosuppressants are infliximab (eg, for colitis) and mycophenolate (eg, for hepatitis). Rescue medications will be sourced per local practice.

## 9 STATISTICAL ANALYSES

### 9.1 Statistical considerations

All statistical analyses will be performed by AstraZeneca or its representatives.

A comprehensive statistical analysis plan (SAP) will be prepared and finalized before first patient in (FPI) and any subsequent amendments will be documented, with final amendments completed prior to reporting of the data. The primary aim of the study is to assess the safety and tolerability of Durvalumab + EP in patients with performance status 0-2.

### 9.2 Sample size determination

This is a safety study and no formal sample size calculation will be done. However, assuming AE of CTCAE grade  $\geq 3$  with an incidence of 60%, approximately 300 patients are needed to achieve the estimation precision no wider than 5.7% based on exact method (Clopper-Pearson). In addition, assuming the imAE with an incidence of 20%, the estimation precision will be no wider than 4.7% using the same method. An illustration of the precision around the varying incidences of AE for the patients enrolled is provided in Table 9.

**Table 9 Precision around varying incidence of AE**

| Sample Size | Precision achieved with different assumed incidence of AE |      |      |      |      |
|-------------|---|------|------|------|------|
|             | 20%   | 40%  | 50%  | 60%  | 70%  |
| 200         | 5.8%  | 7.0% | 7.1% | 7.0% | 6.6% |
| 300         | 4.7%  | 5.7% | 5.8% | 5.7% | 5.3% |
| 500         | 3.6%  | 4.4% | 4.5% | 4.4% | 4.1% |

### **9.3 Definitions of analysis sets**

#### **9.3.1 Safety analysis set (SAS)**

The safety analysis set will include all subjects who received at least one dose of study treatment.

#### **9.3.2 Efficacy analysis set**

The safety analysis set will be used for the efficacy analysis set.

### **9.4 Outcome measures for analyses**

#### **9.4.1 Calculation or derivation of safety variables**

Safety and tolerability will be assessed in terms of AEs, deaths, laboratory data, vital signs, ECG and exposure. These will be collected for all patients.

#### **Adverse events**

Adverse events will be summarized as follows in terms of both Medical Dictionary for Regulatory Activities [MedDRA] preferred terms and CTCAE grade:

**AE:** Number and proportion of patients with AEs in total and by causality and severity

**AE with Grade  $\geq 3$ :** Number and proportion of patients with Grade  $\geq 3$  AEs

**SAE:** Number and proportion of patients with SAEs in total and by causality and severity

**AEs leading to death:** Number and proportion of patients with AEs leading to death

**AEs leading to treatment discontinuation:** Number and proportion of patients with AEs leading to treatment discontinuation

**AESIs:** An adverse event of special interest (AESI) is one of scientific and medical interest specific to understanding of the Investigational Product and may require close monitoring and rapid communication by the investigator to the sponsor. An AESI may be serious or non-serious. Please refer to Section 7.5. In order to further characterize safety objectives related to AESIs, outcome measures will be assessed, which may include (and are not necessarily limited to) the following:

- (a) Number and proportion of patients with AESIs, by pre-defined type (or newly defined by this study) in total and by seriousness, severity and causality, including immune-relatedness;
- (b) Number and proportion of patients who received steroids, immunosuppressants and/or hormone replacement therapy to manage AESIs;
- (c) Time from start of durvalumab (MEDI4736) to the onset of an AESI pre-defined type, all

interventions of AESIs by type of intervention (including intervention with steroids, immunosuppressants and/or hormone replacement therapy), and time from onset of an AESI type to resolution;

(d) Duration of the intervention with steroids, immunosuppressants and/or hormone replacement therapy until the resolution of AESI;

(e) Laboratory findings, vital signs and other safety parameters associated with AESIs will be summarized as part of the AESI outcome measures.

**imAEs:** The imAEs will be assessed as a subset of AESIs. Please refer to Section 7.5.

Any AE occurring before treatment with study drug will be included in the data listings but will not be included in the summary tables of AEs. Any AE occurring within 90 days of discontinuation of durvalumab will be included in the AE summaries.

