#### **4.6 Discontinuation of study treatment**

An individual patient will not receive any further IP (durvalumab + EP or durvalumab monotherapy) if any of the following occur in the patient in question:

- Withdrawal of consent from further treatment with IP. The patient is, at any time, free to discontinue treatment, without prejudice to further treatment. A patient who discontinues treatment is normally expected to continue to participate in the study unless they specifically withdraw their consent to further participation in any study procedures and assessments (see Section 4.7.2).
- An AE that, in the opinion of the investigator or AstraZeneca, contraindicates further dosing.
- An AE that meets criteria for discontinuation of durvalumab as defined in the Dosing Modification and Toxicity Management Guidelines (see section 7.9 and Annex to Protocol).
- Evidence of a new paraneoplastic syndrome(s) or worsening of an existing paraneoplastic

- syndrome(s).
- Pregnancy or intent to become pregnant
  - Noncompliance with the study protocol that, in the opinion of the investigator or AstraZeneca, warrants withdrawal from treatment with IP (eg, refusal to adhere to scheduled visits).
  - Initiation of alternative anticancer therapy including another investigational agent.
  - Clinical progression or confirmed radiological progression per Investigator assessment (refer to Appendix C) and Investigator determination that the patient is no longer benefiting from treatment with IP.
  - EP treatment should be discontinued after a maximum of 6 cycles
  - EP treatment  $\leq$  2 cycles
  - Durvalumab treatment delayed  $>$  12 weeks
- 

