| AE   | X                        | X  | X  | X                                      | X                              |                                       |
| ECOG performance status  | X                        | X  | X  | X                                      | X                              |                                       |
| IP Administration   |                          |  |  |  |                                |                                       |
| Durvalumab h  |                          | X  | X  | X                                      |                                |                                       |
| Etoposide i   |                          | X  | X k                           |  |                                |                                       |
| Carboplatin or cisplatin ij   |                          | X  | X k                           |  |                                |                                       |
| Tumor assessment per Investigator - report (according to RECIST1.1) l | X                        | On study tumor assessments should occur at Week 6±2 weeks, at Week 12±2 weeks then every 8±2 weeks m until PD |  |  |                                |                                       |
| Subsequent anticancer therapy  |                          |  |  |  | X                              | X                                     |
| Survival status  |                          |  |  |  | X                              | X                                     |

a. Written informed consent and any locally required privacy act document authorization must be obtained prior to performing any protocol-specific procedures, including screening/baseline evaluations. If laboratory or imaging procedures were performed for alternate reasons prior to signing consent, these can be used for screening purposes with

consent of the patient. However, all screening laboratory and imaging results must have been obtained within 28 days of first dose.

- b. Any clinically significant abnormalities detected require triplicate ECG results.
- c. Serum or plasma clinical chemistry (including LFT monitoring) and hematology may be performed more frequently if clinically indicated.
- d. If screening laboratory assessments are performed within 3 days prior to Day 1 (first infusion day), they do not need to be repeated at day 1.

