## **7.3 Collection of adverse events**

### **7.3.1 Time period for collection of adverse events**

Adverse events will be collected from time of signature of informed consent throughout the treatment period and including the follow-up period up to 90 days after the last dose of durvalumab treatment. If an event that starts post the defined safety follow up period noted above is considered to be due to a late onset toxicity to study drug then it should be reported as an AE or SAE as applicable.

All SAEs will be recorded and reported to the Sponsor or designee within 24 hours, as indicated in Appendix A. The Investigator will submit any updated SAE data to the Sponsor within 24 hours of it being available.

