**8.2.1 Duration of treatment and criteria for treatment through progression**

All treatment will be administered beginning on Day 1.

Treatment with SoC chemotherapy (EP) will be limited to 6 cycles on a Q3W schedule, at the investigators' discretion.

Durvalumab will be administered beginning on Day 1 until PD unless there is unacceptable toxicity, withdrawal of consent, or another discontinuation criterion is met.

During the treatment period, patients who are clinically stable at an initial RECIST 1.1-defined PD may continue to receive study treatment at the discretion of the Investigator and patient as long as they are deemed to be receiving clinical benefit. A follow-up scan is to be collected after the initial RECIST 1.1-defined PD, 4-8 weeks after the prior assessment of PD.

Patients who continue to receive IP at the discretion of the Investigator can receive treatment until they are no longer deemed to be receiving clinical benefit or end of the study, unless there is unacceptable toxicity, withdrawal of consent, or another discontinuation criterion is met. Image acquisitions and tumor assessments should continue on their regular imaging schedule for the duration of treatment.

Patients with rapid tumor progression or with symptomatic progression that requires urgent medical intervention (eg, central nervous system metastasis, respiratory failure due to tumor compression, spinal cord compression) will not be eligible for continuing durvalumab.

For all patients who are treated through progression, the investigator should ensure patients do not have any significant, unacceptable or irreversible toxicities that indicate continuing treatment would not further benefit the patient.

Patients who AstraZeneca and the investigator determine may not continue treatment after PD will be followed up for survival. Patients who have discontinued treatment due to toxicity or symptomatic deterioration, or who have commenced subsequent anticancer therapy, will be followed up until confirmed disease progression and for survival.

Following confirmed disease progression, standard chemotherapy can be offered by the investigator per local practice.

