### **Objective Response Rate**

Objective Response Rate is defined as the number (%) of patients with measurable disease with at least 1 visit response of CR or PR. Data obtained up until progression or last evaluable assessment in the absence of progression will be included in the assessment of ORR. If any patients do not have measurable disease at baseline then the analysis of ORR will exclude these patients, so that the denominator is a subset of the SS who have measurable disease at baseline.

However, any CR or PR which occurred after a further anti-cancer therapy was received will not be included in the numerator for the ORR calculation.

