## **10.3 Study timetable and end of study**

After patients have discontinued from durvalumab treatment, other available treatment options will be at the discretion of the physician.

Enrolment will be closed as soon as the product receives China marketing authorization as first line treatment for ES-SCLC or total 300 sample size is achieved, whichever comes first.

Treatment will continue to be provided to all patients who are already enrolled to the study and who are still deriving benefit, until disease progress or study end.

The end of the study is defined as “the last visit of the last patient undergoing the study”. The study will be end when all patients have completed follow-up for safety or sufficient maturity for the secondary efficacy objectives has been reached, which will estimate to be end by Q4, 2022.

The study may be terminated at individual centers if the study procedures are not being performed

according to GCP.

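### The 90-day AE window has no cut-off at subsequent anticancer therapy, so the all-cause Grade ≥3 incidence can include first severe events that occur on later drugs

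*Protocol*

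**What the plan says.** Section 9.4.1 fixes which events enter the AE tables. At the late end: "Any AE occurring within 90 days of discontinuation of durvalumab will be included in the AE summaries". At the early end: "Any AE occurring before treatment with study drug will be included in the data listings but will not be included in the summary tables of" adverse events. This pre-treatment rule is the only exclusion given. Section 7.3.1 collects events over a matching period, "including the follow-up period up to 90 days after the last dose of durvalumab treatment", also with no stop at new therapy.

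Three places allow other anticancer treatment inside that period, and none sets a waiting time:

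- Section 8.2.1: "Following confirmed disease progression, standard chemotherapy can be offered by the investigator per local practice".
- Section 10.3: "After patients have discontinued from durvalumab treatment, other available treatment options will be at the discretion of the physician".
- Section 4.6 lists among the reasons for stopping study drug: "Initiation of alternative anticancer therapy including another investigational agent".

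Table 2 has a row "Subsequent anticancer therapy", marked at the 90-day safety visit and in survival follow-up.

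Section 9.5.1 reports the Grade ≥3 incidence with a Clopper-Pearson 95% interval and repeats the table by relationship to treatment. For objective response the protocol does deal with later therapy: "any CR or PR which occurred after a further anti-cancer therapy was received will not be included in the numerator".

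**The concern.** The primary objective concerns how safe and tolerable durvalumab plus EP is in patients with performance status (PS) 0–2. A patient who gets through the study regimen without a Grade ≥3 AE, stops durvalumab, starts another anticancer drug and then has a first severe event within 90 days becomes a case in the headline proportion. The numerator then mixes toxicity during the study regimen with toxicity during whatever followed it.

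The overlap is a foreseeable result of the design. Section 2.2.3 puts the median time to progression in this disease at 4 to 6 months, durvalumab normally ends at progression, and further treatment is then open to the physician. A patient who stops study drug because another therapy has begun spends essentially the whole window on that therapy.

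The rule is written into the protocol and is not left open for the SAP. An SAP that simply replaced the 90-day count with a truncated one would contradict Section 9.4.1. An SAP could add a truncated count, but the protocol neither asks for one nor says which figure would lead.

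**Working it through.** **1. The plan's own precision figures.** Inputs from Section 9.2 and Table 9: N = 300; assumed incidence 60% for Grade ≥3 AEs and 20% for immune-mediated AEs; exact Clopper-Pearson method. Section 9.5 gives the interval as two-sided 95%. Half-width = (upper limit − lower limit)/2.

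- 180/300: 54.2% to 65.6%, half-width 5.69 points (stated 5.7).
- 60/300: 15.6% to 25.0%, half-width 4.68 points (stated 4.7).

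All 15 cells of Table 9 reproduce to one decimal. The normal approximation gives 5.54 and 4.53, so the exact method was used as stated. The sample-size section is sound. The issue is which events are counted.

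**2. How the window changes the count.** Let

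- p0 = incidence if counting stops at subsequent therapy;
- f = share of patients still without a Grade ≥3 AE who start new therapy inside the 90 days;
- q = their risk of a first Grade ≥3 AE after that start and still inside the window.

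Only patients with no earlier Grade ≥3 AE can add to the incidence, so

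full-window incidence = p0 + (1 − p0) × f × q.

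The protocol gives neither f nor q. The ranges below are assumptions: f = 20–60%, q = 10–50%. For p0 the planning value of 60% is used.

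| f | q | Added = 0.40 × f × q | Full-window incidence | 95% CI, N = 300 |
|---|---|---|---|---|
| 20% | 10% | 0.8 points | 60.8% | 54.9–66.2% |
| 40% | 30% | 4.8 points | 64.8% | 59.0–70.1% |
| 60% | 30% | 7.2 points | 67.2% | 61.7–72.6% |
| 60% | 50% | 12.0 points | 72.0% | 66.6–77.0% |

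In the last two rows the interval no longer contains 60%.

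**3. When the shift matches the planned precision.** 0.40 × f × q = 0.057 gives f × q = 0.057/0.40 = 0.1425, or about 0.14.

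**4. The same relation read backwards.** If 60% is what the full window shows, the truncated incidence is p0 = (0.60 − fq)/(1 − fq):

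- f = 20%, q = 10%: (0.60 − 0.02)/0.98 = 59.2%.
- f = 60%, q = 50%: (0.60 − 0.30)/0.70 = 42.9%.

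**5. The other primary endpoint.** Section 7.5 requires an immune-mediated AE to be associated with drug exposure and to have no clear alternative cause. An event plainly due to a later drug fails that definition, so the calculation above is not applied to it.

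**The case against.** The best defence is that the endpoint is coherent as written. Section 7.1 defines an AE regardless of causality, and counting all of them over a fixed 90 days is a legitimate choice that suits late immune toxicity and contradicts nothing else in the protocol. Section 9.5.1 adds a table by relationship to treatment and patient-level listings of Grade ≥3 events, so a reader can see which events the investigator attributed to study treatment.

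Most of this stands, and it is why the 90-day count should stay. The relationship table is only a partial answer. It depends on the investigator's causality judgement, and it also removes unrelated events that occurred during the study regimen. Neither table gives the all-cause Grade ≥3 incidence up to the start of other therapy.

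The contrast with objective response also has limits. PFS is explicitly counted regardless of later therapy, and OS has no cut. The protocol is therefore not inconsistent in leaving safety uncut. For safety it simply does not address the matter.

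The upper end of the assumed ranges may be generous. Sections 8.2.1 and 9.5.4 and Appendix C describe treatment beyond progression in some patients, PFS maturity of about 60% at the primary analysis, and confirmation of progression at least 4 weeks later unless the patient deteriorates. Patients who completed EP without a Grade ≥3 AE may also tolerate later drugs better than average. In addition, the formula treats every severe event after the switch as foreign to the regimen, although some will be delayed durvalumab toxicity.

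Four stronger readings are tempting but are not supported:

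- That the window overlaps later therapy for most patients: the protocol gives no uptake or timing of second-line treatment.
- That the PS 0–1 and PS 2 figures are distorted differently: this is plausible if fitness governs later treatment, but no figure shows it.
- That EP toxicity falls outside a window tied to durvalumab: Section 7.9 concerns temporary holds, events are collected throughout treatment, and no realistic case of loss emerges.
- That the truncated count must be primary: it shortens observation for patients who switch early, which is a bias of its own.

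**Conclusion.** The point holds for the Grade ≥3 endpoint as a reporting weakness that is cheap to repair. It does not make the analysis invalid. The rule in Section 9.4.1 allows first severe events on later anticancer drugs into the all-cause incidence and its interval, and the protocol plans no all-cause figure that would show how many there are. The shift can only be upward, and a larger sample would not reduce it.

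Its size is unknown. The 0.8 to 12.0 points rest on the assumed p0, f and q, so the effect could be negligible or could exceed the planned precision. Immune-mediated AEs are largely protected by their definition. Which of the two windows should lead is open to debate; showing both, with the headline chosen beforehand, settles the matter without deciding it on principle.

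Two smaller matters belong with this. Section 9.4.1 starts the 90 days at durvalumab discontinuation and Section 7.3.1 at the last dose, and these dates can differ. Table 2 lists subsequent therapy but does not mention its start date.

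**What to change.** In Section 9.4.1:

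- Add the Grade ≥3 AE incidence with its Clopper-Pearson 95% CI, overall and for PS 0–1 and PS 2, counted from first dose to the earlier of 90 days after the last durvalumab dose and the day before the first subsequent anticancer therapy.
- Report it beside the full 90-day incidence, and state before the data are analysed which of the two is the headline figure.
- Keep the full 90 days for immune-mediated AEs, and flag those that begin after subsequent therapy has started.
- Use one anchor date for the 90 days in Sections 7.3.1 and 9.4.1.

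Confirm that the eCRF records the start date of subsequent therapy, because the truncated count cannot be derived without it.

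The cost is a few sentences, one extra table and, if the date is not yet collected, one eCRF field. AE collection, safety reporting and patient care do not change. The truncated figure observes early switchers for less time and leaves out late durvalumab toxicity after a switch, so it should appear only together with the 90-day figure.
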